2.2.d. Changes in Mood Scores: Study 2 utilized the Spielberg State Trait Anxiety Inventory (STAI), State and Trait subscales, and the Exercise Induced Feeling Inventory (EIFI) with subscales for Revitalization, Tranquility, Revitalization, and Physical Exhaustion.(56, 57) These scales were selected because they can be given repeatedly to measure current mood states over time. Mood assessments were obtained at baseline, before each scan, and at weeks 4, 8, and 12. Groups did not differ on demographic variables or STAI Trait anxiety scores. Tonic changes over the course of the study (Scan 2 – Scan 1) for mean mood scores showed significant increases in the yoga group for Revitalization (1.8 ± 2.5 , $t_{18} = 3.21$, $p = 0.005$). Acute changes from pre- to post-intervention (Scan 3 – Scan 2) for mean mood scores showed significant increases in the yoga group for Revitalization (2.5 ± 2.7 , $t_{18} = 4.12$, $p < 0.001$) and Tranquility scores (2.0 ± 1.8 , $t_{18} = 4.77$, $p < 0.001$), and a significant decrease in STAI-State anxiety scores, consistent with decreased anxiety (-5.2 ± 5.5 , $t_{17} = -4.05$, $p < 0.001$). A Generalized Estimating Equation (GEE) analysis of mean mood scales at baseline, and weeks 4, 8, and 12, showed the yoga group to have significantly greater improvement than the walking group on all subscales of the EIFI, with significant increases in Tranquility, Revitalization and Positive Engagement, and significant decreases in Physical Exhaustion.

2.2.e. Study 3 (9), Streeter et al 2012⁹: This study compared GABA/Cr in subjects with MDD who were enrolled in a 12-week trial of Hatha yoga for low back pain (Saper 2009) and with healthy controls from Study 2.(58) Iyengar yoga is a subset of Hatha yoga. The Iyengar yoga 12-week intervention from Study 2 and the Hatha yoga 12-week intervention for Low Back Pain were reviewed by a certified Iyengar instructor and found comparable. The MRS protocols used to collect GABA/Cr were identical in both studies. This allowed Scan 1, obtained before the 12 week interventions and Scan 2 after the interventions to be compared in healthy controls ($n=19$) from Study 2 and subjects with MDD and low back pain from Study 3 ($n=2$). At baseline, the MDD subjects with low back pain demonstrated lower GABA/Cr, which increased over the course of the 12-week yoga intervention, as depressive symptoms and low back pain declined.

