2.2.m. Parasympathetic tone measured with Respiratory Sinus Arrhythmia (RSA) (Figure 5): In Study 4, RSA values were derived from an electrocardiogram (ECG) recording over a three stage protocol: 1) a 5-minute rest, 2) a 3-minute step test that removes the vagal break, and 3) a 5-minute recovery period. RSA was measured at baseline and after an intervention at weeks 4, 8, and 12. No differences between the HDG and LDG were observed for baseline or recovery RSA. A GEE analysis of changes over the 12-week intervention for the full cohort showed no RSA differences at rest ($\beta = -0.01$, $z = -0.74$, $p = 0.46$), but an increase in RSA during recovery ($\beta = 0.05$, $z = 2.12$, $p = 0.03$), consistent with the recovery stage being the best marker of tonic changes from the beginning to the end of the study. Midway through the study, an additional RSA was added pre the week-12 intervention, permitting comparison of pre- and post- week-12 intervention RSA values (n=16). Rest stage ($F_{1,15} = 11.06$, $p = 0.005$) and recovery stage changes ($F_{1,15} = 3.82$, $p = 0.07$) were significant from pre- to post- 12-week intervention. The acute changes in both rest and recovery stages observed from pre- to post-intervention, support the hypothesis that yoga acutely increases resilience measured by increased RSA in the rest and recovery stages. Tonic changes were only significant in the recovery stage, suggesting that the recovery stage is more sensitive to resilience.

2.2.n. Correlation of Thalamic GABA/Cr and RSA: Because the proposed study will use two yoga classes per week, correlational analysis of GABA and RSA was conducted on data from the LDG. Acute changes in GABA were measured at the end of the 12-week intervention from pre-yoga intervention (Scan 2) to post-yoga intervention (Scan 3). At the end of the 12-week yoga intervention, acute RSA changes were also

[figure not shown]

Figure 3: Thalamic spectra showing increased GABA (LDG Subject), Scan 1 pre-randomization to Scan 2 after a 12-week yoga intervention to Scan 3 immediately after a 90-minute yoga and breathing intervention.

[figure not shown]

Figure 4: Thalamic GABA/Cr in healthy controls and patients with MDD at baseline (Scan 1), after 12-week yoga intervention (Scan 2) and immediately after a yoga intervention (Scan 3). GABA increases in subjects with MDD, and differences between MDD and controls decreases.

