Figure 5: Respiratory Sinus Arrhythmia (RSA) at rest and recovery (after step challenge). Significant changes observed pre-12 week (blue dash, $F_{1,15}=11.06$, $p=.005$) and post-12 week (red solid, $F_{1,15}=3.82$, $p=.07$) yoga intervention.

measured before and immediately after a yoga intervention. A Spearman rho correlation (two-tailed) of the difference between this 12 week pre- and post- intervention recovery RSA for Scan 3 – Scan 2 GABA/Cr was statistically significant ($\rho = .821$, $p = 0.023$). This supports the hypothesis that RSA is significantly correlated with GABA.

2.2.o. Safety and Reduced Suicidal Ideation under review Streeter: In Study 4, mild side effects related to the study occurred, most commonly muscle soreness ($n=13$), which resolved over the course of the study. There were no serious Adverse Events related to the study. No subjects developed suicidal ideation during the study; 9/10 subjects reporting suicidal ideation without intent at screening on the C-SSR, with 8/9 reporting the resolution of this symptom over the course of the study. This preliminary evidence suggests that yoga and coherent breathing are safe and effective in the treatment of MDD, and may reduce suicidal ideation.

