variance with independent groups. We used nQuery Advisor, version 7.0 for these computations. Using GABA level as the dependent variable of interest and employing the observation from Study 2 in which the walking intervention showed no change in GABA over the 12-week intervention, it is predicted that GABA levels will not change over time in the walking group. We hypothesize that the yoga group will show mean GABA/Cr = 0.28, 0.285, and 0.32 at the three study time points and that the walking group will show mean GABA/Cr = 0.28, 0.28, and 0.28. Assuming a common standard deviation at each time point of 0.06 and a within-subject correlation of 0.65, we will have 80% power to detect the above noted pattern of repeated mean GABA/Cr with a two-sided alpha of 0.05. With the same data configuration, we will have 85% power should the within-subject correlation be as high as 0.70.

3.5.4. Tonic changes in Recovery RSA from screening to 12 weeks: The GEE of changes in recovery RSA in the full cohort (n=27) over 12 weeks was significant in Study 4; however, only the recovery RSA values in the smaller LDG (n=14) were used for the power analysis, as this reflects the dosage that will be utilized in the proposed study. While the repeated measures ANOVA did not reach statistical significance in the LDG (screening mean = 7.7 ± 2.5 and 12 week mean = 8.2 ± 2.9 , $F_{1,12} = 1.094$, $p = 0.315$), a post hoc power analysis was conducted, which determined that the achieved effect size was $f = 0.291$, with 52% power. Based on this same small to medium effect size, an a priori power calculation that includes two groups (yoga and walking) was conducted, which determined that **n=34** subjects would be necessary to detect significant differences in RSA at effect size $f = 0.291$, with 90% power.

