3.5.5. Acute changes in RSA at 12 weeks (pre and post yoga intervention): Half way through Study 4, an RSA collection was added prior to the 12-week yoga intervention, which allowed acute changes in RSA to be calculated. An ANOVA of rest stage changes reached statistical significance; 12-week pre intervention resting mean = 4.9 ± 1.8 and 12-week post intervention resting mean = 5.7 ± 1.6 ($F_{1,14} = 11.056$, $p = .005$). A post hoc power analysis was conducted, which determined that the achieved effect size was $f = .858$, with 99% power. Based on this same large effect size, an a priori power calculation was conducted, which determined that **n=10** subjects would detect significant differences at effect size $f = .858$, with alpha = .01 and two groups (yoga and walking) would achieve 90% power. An ANOVA of rest stage changes reached statistical significance; 12 week pre intervention recovery mean = 6.7 ± 2.4 and 12 week post intervention recovery mean = 8.1 ± 3.4 ($F = 3.819$, $p = 0.070$). A post hoc power analysis was conducted, which determined that the achieved effect size was $f = 0.504$, with 96% power. Based on this same large effect size, an a priori power calculation was conducted, which determined that **n=20** subjects would detect significant differences at effect size $f = 0.504$, with $\alpha = .01$ and two groups (yoga and walking) would achieve 90% power.

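### The recovery-RSA gain that sizes the Aim 3 tonic test was read after a yoga session, so it cannot be separated from the acute session effect, and Hypothesis 3a repeats the problem

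*Protocol*

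**What the plan says.** **Timing in Study 4 (Protocol 2.2.m, 2.2.n).** "RSA was measured at baseline and after an intervention at weeks 4, 8, and 12". Midway through, "an additional RSA was added pre the week-12 intervention, permitting comparison of pre- and post- week-12 intervention RSA values (n=16"). Section 2.2.n describes the week-12 pair as "measured before and immediately after a yoga intervention".

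**Interpretation (2.2.m).** The full-cohort GEE found no change at rest and a rise in recovery, which the protocol reads as "consistent with the recovery stage being the best marker of tonic changes from the beginning to the end of the study".

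**Sizing (3.5.4).** "only the recovery RSA values in the smaller LDG (n=14) were used for the power analysis". The inputs are "screening mean = 7.7 ± 2.5 and 12 week mean = 8.2 ± 2.9", leading to f = 0.291, n=34 and 90% power. Sections 3.3.2.2 and 4.5.2.9 carry Aim 3 forward as 68 completers.

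**Acute change (3.5.5).** "12 week pre intervention recovery mean = 6.7 ± 2.4 and 12 week post intervention recovery mean = 8.1 ± 3.4".

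**Planned test (3.5, Hypothesis 3a).** The yoga group, but not the walking group, is expected to show a tonic increase in recovery RSA, with the reading specified as post-intervention. In Table 3, RSA 1 precedes Scan 1 and follows no session, RSA 6 and RSA 7 fall before and after the week-12 session, and RSA 8 precedes Scan 2. The SAP (D.17) names no RSA contrast.

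**Use of the word elsewhere (2.2.d).** For Study 2 mood, the protocol writes of "Tonic changes over the course of the study (Scan 2 – Scan 1) for mean mood scores", a contrast with no session just before either reading, and keeps acute for the change across a session.

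**The concern.** A tonic change should still be present when no session has just taken place. The pilot change labelled tonic has a session immediately before its second reading and none before its first, so one session could produce it without any lasting shift in vagal tone.

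Two things are at stake. The 90% power for a tonic RSA change rests on an effect whose tonic part is unknown. And a positive result on Hypothesis 3a could be reported as a lasting change over 12 weeks, which is how Hypothesis III in section 1.0 frames it, when it reflects the session completed just before RSA 7. Randomization does not remove this. The walking arm cancels the acute part only if yoga with paced breathing and walking have equal acute effects on RSA, and the protocol's rationale expects yoga to have a distinct one.

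**Working it through.** **1. Reproduce the plan's figure.** Inputs: f = 0.291, two groups, 90% power (3.5.4); alpha = 0.05 (general statement in 3.5.1). Assumed, because 3.5.4 does not state them: m = 2 time points and within-subject correlation 0.5. For the repeated-measures F test, λ = f² × N × m / (1 − ρ).

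- N = 34: λ = 0.0847 × 34 × 2 / 0.5 = 11.5 on 1 and 32 df, power 90.8%.
- 34 is the smallest even N reaching 90%. The stated n=34 is therefore reproduced as a total for two groups.

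**2. Is the week-12 value of 8.2 post-session?** Section 3.5.4 does not say, but 2.2.m describes no other routine week-12 reading. The pre-session reading came late: the Spearman correlation in 2.2.n (0.821, p = 0.023) corresponds to about 7 low-dose subjects with a pre/post pair, too few to supply the 14 values in 3.5.4. The post-session means also agree, 8.2 in the low-dose group and 8.1 in the paired subset.

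**3. Compare the sizes (recovery RSA).**

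| Contrast | Sample | Change |
|---|---|---|
| Screening to week 12, post-session (called tonic) | low-dose group, n=14 | 8.2 − 7.7 = +0.5 |
| Week 12, pre- to post-session (acute) | paired subset, n=16 | 8.1 − 6.7 = +1.4 |
| Week-12 pre-session minus screening | n=16 against n=14 | 6.7 − 7.7 = −1.0 |

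The acute change is 1.4 / 0.5 = 2.8 times the gain called tonic.

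**4. What the third row can bear.** The 16 are not restricted to the low-dose group, and no paired change is reported. Treating the samples as independent (they probably overlap), SE = √(2.5²/14 + 2.4²/16) = 0.90, and the 95% CI is −1.0 ± 1.96 × 0.90, about −2.8 to +0.8. It includes zero and the planned +0.5.

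**5. Power by assumed tonic share.** Scale f by the share and keep the other inputs of step 1.

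| Tonic share of the +0.5 | Power, N=34 | Power, N=68 | N for 90% |
|---|---|---|---|
| 100% | 91% | 99.7% | 34 |
| 75% | 69% | 94% | 58 |
| 50% | 38% | 66% | 128 |
| 25% | 13% | 22% | 500 |

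**6. A detectable difference that needs no pilot effect.** The SD of change implied by 3.5.4 is 0.5 × √14 / √1.094 = 1.79. For a two-sample t-test of changes with 34 per arm at two-sided 0.05, power is 21% for a between-arm difference of 0.5, 62% for 1.0 and 81% for 1.25. This assumes that 1.79 also holds for change to a pre-session reading. The 1.25 follows from the SD and the sample size; it does not measure the acute confound.

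**The case against.** **The sizing matches the endpoint as worded.** Hypothesis 3a names post-intervention recovery RSA, and Study 4 measured that contrast. This stands: 3.5.4 does not size a different endpoint from the one in 3a. The defect lies in calling that endpoint tonic and in what would be concluded from it.

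**The usage in 2.2.d concerns Study 2 mood scores.** It does, and it is not a protocol-wide definition. The point does not depend on it, since the confound follows from the reading times.

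**A reader might infer that Study 4 shows no tonic rise, or a fall, because 6.7 lies below 7.7.** The documents do not support this. The samples differ and the interval in step 4 allows a rise. Nor is it shown that the gain is wholly acute: its tonic share is unknown.

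**Some pilot evidence points the other way.** The GEE includes three post-session readings, so part of its trend compares like with like, although the split is not reported. Resting RSA rose acutely (4.9 to 5.7) yet showed no change over 12 weeks, which does not fit a simple acute carry-over. Both observations stand, and neither isolates a tonic change.

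**The practical effect is small.** EIFI, not RSA, sets n=70; at 68 a 75% tonic share still gives 94% by the protocol's method; and Hypothesis 3b examines pre-to-post differences separately. This limits the consequence to the power claim and the interpretation of Aim 3.

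**Conclusion.** The point holds as one of confounding. The +0.5 behind f = 0.291, n=34 and 90% power combines any lasting change with an acute session effect that was +1.4 in the paired subset and could account for all of it. The protocol reports no estimate of tonic RSA change free of that effect, so the 90% applies to tonic change only if the whole gain is tonic. Hypothesis 3a carries the same ambiguity into the trial's conclusions.

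This rests on reading the 8.2 in 3.5.4 as post-session, which 2.2.m strongly implies but 3.5.4 does not state. The power figures by tonic share further assume the protocol's method with correlation 0.5 and alpha 0.05, and the 1.25-unit figure assumes an SD of change of 1.79 for pre-session readings.

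**What to change.** 1. **Hypothesis 3a, and the SAP to match:** define the tonic contrast as the between-arm difference in change in recovery RSA from RSA 1 to one pre-session recording, RSA 6 or RSA 8, named before any unblinded analysis. Keep the change from RSA 1 to RSA 7 as a separate baseline-to-post-session contrast under that name.
2. **Sections 2.2.m and 3.5.4:** relabel 7.7 to 8.2 as baseline-to-post-session, and qualify the statement that recovery is the best tonic marker by adding that Study 4 cannot separate it from the acute effect.
3. **Section 3.5.4:** state that the 90% holds only if the whole gain is tonic. Give instead the detectable difference: about 1.25 units between arms with 80% power at 34 per arm, assuming an SD of change of 1.79 for pre-session readings.

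The cost is wording and a less favourable power statement. All the recordings are already in Table 3, so no visit or procedure is added, and the overall n=70 is unchanged.

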3.0 RESEARCH DESIGN AND METHODS

3.1 Drug/Device Information: NOT APPLICABLE

3.2 Type of Study: (Table 3: Individual Timeline): This is a longitudinal, efficacy randomized controlled trial (RCT). Veterans with MDD will be evaluated for eligibility and randomized to a 12-week intervention of a twice-weekly yoga and coherent breathing or walking group. As there is evidence that exercise improves mood in unipolar depression, the walking group will serve as an active control condition.(47) The policy for Common Data Elements will be incorporated into the data collection matrix. The Consolidated Standard of Reporting Trials (CONSORT) will be used to ensure the quality of reporting for this RCT.(48) The **primary dependent variable** will be changes in the Hamilton Depression Rating Scale (covering a 2 week period), and mood and anxiety scales (designed for repeated use, such that changes from pre to post intervention can be gauged), measured using valid and reliable psychological instruments obtained at screening, intervention weeks 4, 8, and 12, and before each MRS scan. The **secondary dependent variable** will be brain gamma amino-butyric acid (GABA) levels measured by magnetic resonance spectroscopy (MRS) in the left thalamus, the same region used in our prior studies.(9, 53, 65) The thalamus has the technical advantage of providing high quality spectra, has a high concentration of GABAergic neurons, and thus a high GABA signal, in which changes can be detected. The thalamus is also anatomically connected to other regions of interest. GABA levels will be measured by MRS in 3 separate scan acquisitions: before randomization (Scan 1), after 12-weeks of the yoga or walking intervention (Scan 2), followed immediately by the group assigned intervention and the final scan (Scan 3). The **third dependent variable** will be respiratory sinus arrhythmia (RSA) a component of heart rate variability (HRV) that is an accurate index of vagal influences on the heart.RSA will be measured before each scan and before and after an intervention at week 4, week 8 and week 12. Medications also are evaluated at weeks 4, 8, and 12. Two and six month follow-up phone calls will assess depression, quantity of yoga practice, and barriers to practice.

3.3.1. Sub-Study Participation: This is not a multisite study. There will be a contract with the McLean Hospital for goods and services regarding the imaging component of this study.

3.3.2. Study Related Procedures

3.3.2.1. Instruments: The following reliable and valid instruments will be used during the screening interview to determine eligibility, and to monitor subjects during the interventions:

- (1) Structured Clinical Interview for DSM-5 (**SCID-5**) is a widely used valid psychiatric diagnostic instrument used to screen for Axis I disorders(66);
- (2) **Columbia Suicide Safety Rating Scale (C-SSRS)** is a clinically administered instrument to assess suicide risk(67);
- (3) **Physical Activity Recall (PAR)** is a widely used structured interview that yields a weekly record of physical activity using Metabolic Equivalents (METs), a method of assessing an individual's level of physical activity in a common unit that can be calculated from a variety of activities.(55) The PAR will be obtained each week of the intervention in the event physical activity becomes a confounding factor.
- (4) **Hamilton Rating Scale for Depression (HDRS)** is a 17-item clinician administered scale frequently used to evaluate the effectiveness of antidepressants being assessed for FDA approval(68);
- (5) **Beck Depression Inventory (BDI-II)** is a 21-item self-administered instrument designed for the assessment of depressive symptoms, with higher scores reflecting greater severity(69);
- (6) **Spielberger State-Trait Anxiety Inventory (STAI)** is a self-administered instrument designed for assessment of trait anxiety (STAI-Trait) and serial assessments of state anxiety (STAI-State) with higher scores indicating higher anxiety(56);
- (7) **Clinician Administered Posttraumatic Stress Scale (CAPS)** is the gold standard clinician administered assessment for PTSD(70);
- (8) **PTSD Check List – Civilian (PCL-C)** is a 17-item self-administered scale corresponding to Diagnostic and Statistical Manual of Mental Disorders (DSM) IV criteria for PTSD. Because not all Veterans have combat experience and not all trauma is from a military experience, the civilian version of the PCL will be used. The use of the CAPS and PCL-C will allow assessment of severity of PTSD symptoms, and if present, will be modeled in statistical analyses;
- (9) **Exercise-Induced Feeling Inventory (EIFI)** is a self-administered instrument designed to assess four distinct feeling states associated with bouts of physical activity: Revitalization, Tranquility, Positive Engagement, and Physical Exhaustion.(57)
- (10) **Pittsburgh Sleep Quality Index (PSQI)** is a self-administered instrument that assesses 9 factors of sleep over a month period, providing a composite score, with higher scores indicating poorer sleep quality.(71)
- (11) **Timeline Follow Back (TLFB)** will be used to assess alcohol consumption for three months prior to screening.(72) A format similar to the TLFB will be used for nicotine consumption.
- (12) **Brief Pain Inventory**, an eleven point Likert Scale of pain intensity will be used to assess pain over the last 24 hours.
- (13) **Stroop Color-Word Test** is a selective attention and inhibitory cognitive control task.(74)

Individual Time Line	Table 3: Individual Time Line and Collection of Dependent Variables		
	Aim 1	Aim2	Aim 3
Individual Time Line	Depression Scales	Mood Scales	GABA RSA
Telephone Screen			
Screening Session	HDRS/BDI-II 1		
3T Brain Scan			
MRS Imaging Session 1			
Pre Scan 1 Measures	HDRS/BDI-II 2	EIFI & STAI 1	RSA 1
MRS Scan 1(Baseline)			GABA 1
Randomization			
Week 4			
Pre-Week 4 Evaluation		EIFI & STAI 2	RSA 2
Week 4 Intervention			
Post-Week 4 Evaluation	HDRS/BDI-II 3	EIFI & STAI 3	RSA 3
Week 5-7 Intervention			
Week 8			
Pre-Week 8 Evaluation		EIFI & STAI 4	RSA 4
Week 8 Intervention			
Post-Week 8 Evaluation	HDRS/BDI-II 4	EIFI & STAI 5	RSA 5
Week9-11 Intervention			
Week 12			
Pre-Week 12 Evaluation		EIFI & STAI 6	RSA 6
Week 12 Intervention			
Post-Week 12 Evaluation	HDRS/BDI-II 5	EIFI & STAI 7	RSA 7
MRS Imaging Session 2			
Pre Scan 2 Evaluation	HDRS/BDI-II 6	EIFI & STAI 8	RSA 8
Scan 2			GABA 2
Interscan Intervention			
Pre-Scan 3 Evaluation		EIFI & STAI 9	RSA 9
Scan 3			GABA 3
Follow-Up 2 month	HDRS/BDI-II 6	EIFI & STAI 10	
Follow-Up 6 month	HDRS/BDI-II 6	EIFI & STAI 11	

(14) **Digit Symbol Substitution Test (DSST)** is one of the frequently used tests to measure psychomotor slowing, and is clinically sensitive because it makes demands on several processes, including perception, working memory, sustained attention and visuomotor co-ordination (Wechsler 1997).

(15) **Child Trauma Questionnaire (CTQ)** is a self-report measure of childhood trauma. (73) This scale will be given during the Week 4 evaluation at the end of the session.

Unless otherwise stated, instruments 4-12 are used at screening, week 4, 8, and 12. In addition, the EIFI and STAI-State are administered before and after interventions at weeks 4, 8, and 12 and before each scan. The CAPS is administered at screening and at week 12. The following instruments are given at Imaging Session 1 & 2: 2, 5, 13, and 14.

Recruitment Plan and Requirements (Table 4): Veterans will be recruited from the Bedford VA Medical Center (VABHCS) through posters, the internet, providing flyers to clinics, in meetings with staff, and recruitment at clinics affiliated with the VABHCS. Veterans who had a diagnosis of depression in the previous two years at the VABHCS will be identified via electronic health records. Targeted letters signed by the PI describing the study and inviting the Veterans to call or mail for more information will be mailed to Veterans. The mailing will include opt-in or opt-out card with postage and/or an opt-in or opt-out phone number. If a card or phone is not received within 10 days of the mailing, the identified Veterans will be called concerning their interest in the study. Data Access Request Tracker (DART) and VA Informatics and Computing Infrastructure (VINCI) will be used to identify potential subjects.

3.3.2.2. If interested they will be provided information about the study and will be allowed to proceed to the telephone interview. These techniques have been used successfully in previous VABHCS studies of yoga interventions.(59) The VABHCS Institutional Review Board (IRB) will pre- approve all forms of advertisement. Current VA policy does not allow email communications as part of the recruitment procedures. Sample size calculations, based on power analyses, require the following number of completers equally divided between the yoga and walking groups to test the hypotheses for each dependent variable: **n=70** completers to test Aim 1: Depressive Symptoms and Mood Scale; **n=56** to test Aim 2: GABA changes; and **n=68** to test Aim 3: RSA changes [D.20]. To meet the criteria for each Aim/Dependent Variable n=70 subjects will complete the intervention with n=56 having usable MRS data. Using data from Study 4, with consideration of changes in inclusion and exclusion criteria and research setting, the following recruitment schedule will be required during a 5-year study period, which will include over 4 years of recruitment and treatment. The required total recruitment and annual requirements at each stage are as follows: telephone screen=420 total or 105/year; screening interview=173 total or 43/year; randomization=100 total or 25/year; and completers=68 total or 18/year.

3.3.2.3. Participation in Non-Assigned Group: A Retention Plan: Prior to randomization, subjects will be asked their group of choice (i.e., yoga or walking), as not being assigned to a group of choice could influence dropout rate. In order to retain subjects not assigned to their choice, subjects will be allowed to participate in the group they are not assigned to for 16 sessions or 8 weeks (i.e., the second intervention), whichever comes first, if they complete their randomized intervention and 14 week follow up phone call. Retention in the randomized intervention is given priority over contamination of the 6-month follow up with the 2nd intervention. There will be no difference in how subjects in the randomized intervention or second intervention will be monitored during the first eight weeks of the intervention. Subjects will not be paid for class attendance or evaluations during the 2nd intervention nor will they undergo MRS scanning. These data are exploratory.

3.3.2.4. Screening: Subjects will be screened by telephone to prevent subjects from coming to the screening interview, only to be excluded based on information that could be obtained over the phone. Telephone questions do not include questions about self-harm or risk of danger. Telephone questions do include questions about metal and implanted medical devices that could preclude MRI scanning. If subjects meet telephone-screening criteria, they will be invited for an in-person screening interview at

the VABHCS. Subjects will be provided with the written consent to review prior to the screening interview. Written informed consent approved by the ENRM VA IRB will be obtained by research staff, defined as being able to assess participants using the Hamilton Depression Rating Scale(HDRS), the Clinician Administered Posttraumatic Stress Scale (CAPS) and assessing subjects for safety issues using the Columbia Suicide Severity Rating Scale (C-SSRS). All subjects will be consented by the PI who will conduct a medical history, physical exam and MRI safety screening prior to scanning. After the informed consent is signed, but before data collection, subjects will take a quiz to assess their knowledge of the study and undergo a breathalyzer test to determine Breath Alcohol Concentrations (BrAC). If BrAC is not zero or the subject fails to demonstrate knowledge of the study on the quiz, subjects will not be allowed to participate in study activities. If the subject answers a quiz question incorrectly, that question will be discussed with the subject, after which the subject will initial the correction. If the study clinician determines the subject does not understand the protocol, including risks of non-conventional therapy, this would constitute reason for exclusion. The PI will review the inclusion/exclusion criteria to determine eligibility prior to the subject being invited to participate in the study.

Potential participants are excluded for a history of psychosis, bipolar illness, and suicidal ideation with intent or a suicide attempt within the last year. Axis-I disorders that would interfere with study participation are exclusionary such as Obsessive Compulsive Disorder or Agoraphobia that would prevent attendance at the intervention. Alcohol Use Disorders with more than 3 DSM-IV criteria. Substance Use Disorders in Remission are allowed. Because inversion can increase intraocular pressure, individuals with a retinal hemorrhage or glaucoma cannot participate unless they receive clearance from their ophthalmologist. Neurologic conditions, which would effect scan results, are exclusionary such as stroke, seizures, brain surgery, HIV and other CNS disorders. The ability to participate in both interventions is required, such that a person who walks with a cane would not be enrolled as it would be a concern that they would either not be able to walk at 2.5 miles an hour for one hour or that if they did it could potentially harm them. Individuals with a history of spine surgery could be excluded depending on the surgery. Individual with cardiovascular or respiratory disease would require careful evaluation that could include a discussion with their physician. Traumatic Brain Injury with greater than 30 minutes loss of consciousness would be exclusionary. During the screening process, the potential participants have to complete a 3-minute step test (See Step Protocol). If the participant is unable to perform the step test, they would be excluded from the study. If during the physical exam, the PI is concerned about the potential participants ability to participate, they maybe asked to attempt to touch their toes, and to get down and then up from a yoga mat or to walk the circuit that they would walk during the walking intervention.

3.3.2.5. Inclusion Criteria:

- (1) male and female Veterans ages 18 to 65;
- (2) Fluent in English;
- (3) Understands the risks and benefits of the study as listed in the Post Consent Quiz
- (4) Females must agree to use an acceptable form of birth control [see 4.6.1.15 for acceptable contraception] and do not intend to become pregnant during the study
- (5) Females have a negative pregnancy test or a serum progesterone in the non luteal stage defined by less than or equal to 1.3 ng/ml prior to Scan 1.
- (6) Meets criteria for MDD on the SCID-5
- (7) Hamilton Rating Scale for Depression (HDRS) scores \geq to 14 at screening
- (8) If subjects have been taking antidepressants that target a monoamine system, the dose has been stable for at least one month with no anticipated changes during the study; or no antidepressants for one month
- (9) If subjects have been in a stable form of psychotherapy for three months, with no anticipated changes in their psychotherapy during the study (this would exclude time-limited manual-driven therapies such Cognitive Behavioral Therapy); or no psychotherapy for three months
- (10) Reliable contact information provided
- (11) Subject weighs up to 300 lbs. at the discretion of the PI.

(12) Subject has completed all required screening instruments and evaluations

3.3.2.6. Exclusion Criteria:

- (13) History of psychosis (substance-induced psychotic disorder and psychotic disorder due to another medical condition are allowable if fully resolved)
- (14) History of bipolar illness
- (15) History of suicidal ideation with intent in the last year according to the Columbia Suicide Safety Rating Scale (C-SSRS)
- (16) Subject has a history of suicidal attempt with intent to injure in the last year according to the C-SSRS.
- (17) Desire to be treated for MDD with a new treatment during the study such as pharmacotherapy somatic therapy or psychotherapy.
- (18) A contraindication to magnetic resonance evaluation (e.g., pregnancy, a cardiac pacemaker, ferrous implant including shrapnel, or intrauterine devices (IUDs) with copper, claustrophobia that would prevent scanning, some tattoos with black ink on the head including permanent eyeliner).
- (19) Current mind-body practice (e.g., yoga, Tai Chi, Qigong, breathing practices, or meditation) defined as more than 6 one-hour sessions in the last 6 months.
- (20) The use of intra-uterine devices with progesterone that interferes with the ability to determine the non-luteal phase required to schedule Imaging Session 1.
- (21) Participates in physical exercise > 5 hours/week that is equivalent to or greater than 6 metabolic equivalents (METs) in intensity.
- (22) Has been treated psychotropic medications such as mood stabilizers (e.g., Valproic Acid, Carbamazepine, or Lithium) in the last three months.
- (23) Subject has been treated a) with a scheduled dose of anti-anxiety agents (e.g., benzodiazepines) or sleeping aids (e.g. Ambien or sedative hypnotics) or b) with pain medication other than Non-Steroidal Anti-Inflammatory Drugs (NSAIDS) in the last one month except for procedure related pain management (e.g., dental procedures).
- (24) Has greater than three current criteria for Alcohol or Substance Use Disorder using DSM-V criteria.
- (25) Does not have a period of 48 hours of no alcohol use on TLFB to participate in scanning given the effects of alcohol consumption on the GABA.
- (26) Has a neurologic condition, such as a Traumatic Brain Injury (TBI) with a loss of consciousness of greater than 30 min, that in the opinion of the PI could compromise subject safety or the integrity of the study.
- (27) Has a medical condition that in the opinion of the PI could compromise subject safety or the integrity of the study.
- (28) Subject would not be expected to complete the study including scheduling issues.
- (29) Has an Axis-I diagnosis, other than depression except as listed, that in the opinion of the PI would interfere with the subject's participation in this study.
- (31) Has participated in another research study in the last 3 months that could affect the dependent variables.
- (32) Must have a period of 24 hours of no nicotine use on TLFB to participate in scanning or nicotine use as allowed by CSD&R Project Manager.
- (33) Subject does not agree to study procedures designed to protect against COVID-19 and the requirements of the virtual interventions.

3.3.2.7. Randomization: Group assignments will be conducted using permuted block randomization with varying block sizes. Block sizes will be multiples of the number of treatments and take the allocation ratio into account. For this study with a 1:1 randomization of 2 groups (yoga and walking), block sizes will be 2, 4, and 6. Randomization will be computer generated with each randomization assignment put on a card in numerically labeled envelopes that will be sealed. The envelopes will be opened in sequential order at the time of randomization by a member of the staff that is not blinded to group assignment. Subjects who want more time to think about participation can be randomized within 12 days of the last screening assessment, with the interventions starting within 7 days.

3.3.2.8. Group Assignment, & Blinding: All investigators are blind to group assignment prior to randomization. Blinding will be guided by the Cochrane Collaboration Tool for assessing risk of bias in randomized trials.(14) The study physicist, [name], and [name], the RSA expert, will be blind to group assignment. Investigators who administer subjective instruments (i.e., Hamilton Rating Scale for Depression and CAPS) will be blind to group assignment. Subjects will fill out self-reporting mood and psychological scales in paper form that will be entered into the VA network by research staff. All VA paper documents with sensitive information will be secured in a locked filing cabinet in a designed VA Office. ECG data used for RSA analysis and MRS data will be labeled with a blinding code provided by the Data Coordinating Center, such that ECG data and MRS data are stripped of identifying information, including removal of study ID, date of acquisition and timing of the assessment (baseline, pre or post the intervention at weeks 4, 8, or 12) before being sent [name] for analysis. As subjects are not blind to the intervention, there is no procedure to break the blind for clinical reasons.

3.3.2.9. Gender Differences: While we will equally recruit both genders, due to the demographics of the VABHCS population, it is anticipated that more males will be recruited, which will provide much needed information on the efficacy of this intervention in men. Due to the influence of menstrual cycle phase and associated changes of progesterone on brain GABA/Cr levels, serum levels of progesterone will be drawn before each scan, with progesterone levels less than or equal to 1.3 ng/ml being considered the non-luteal stage, a stage when GABA/Cr is not influenced by menstrual cycle.(75) Serum progesterone levels will be drawn at the VABHCS.

3.3.2.10. Subject Compliance and Payment: Compliance with group session attendance and homework is important, both as an assessment of treatment acceptance and as a measure of the "dose" of the intervention required for symptom reduction. Attendance at the interventions will be recorded on an attendance sheet; home practice of yoga and walking will be recorded on the weekly PAR. Subjects will be paid for their time: \$10 for each group session, \$20 for the week 4 evaluations, \$40 for the week 8 evaluations, \$60 for the week 12 evaluations, and \$40 for each MRS scan for a maximum of \$480.

